**PARTNERS HUMAN RESEARCH COMMITTEE
DETAILED PROTOCOL**

PRINCIPAL/OVERALL INVESTIGATOR

[name].

PROTOCOL TITLE

A Randomized Controlled Trial of an Advanced Care Planning Video Decision Support Tool for Patients with End-Stage Liver Disease (Clinicaltrials.gov Identifier NCT03557086)

FUNDING

NIH-NIDDK National Institute of Diabetes and Digestive and Kidney Diseases
4K24DK078772-10

VERSION DATE

Version 9: February 6, 2020

A Randomized Controlled Trial of an Advanced Care Planning Video Decision Support Tool for Patients with End-Stage Liver Disease

Version 9: February 6, 2020

SPECIFIC AIMS

The goal of this pilot randomized trial is to assess the feasibility and preliminary efficacy of an advanced care planning (ACP) video decision support tool for improving patients' knowledge regarding their goals of care options and end of life (EOL) decision-making in patients with end-stage liver disease (ESLD).

Aim 1: To assess the feasibility and acceptability of an ACP video decision support tool for patients with ESLD

- *Hypothesis 1: The intervention will be deemed feasible and acceptable if at least 60% of eligible patients are enrolled in the study and if at least 60% of patients randomly assigned to the video intervention report that the video is acceptable*

Aim 2: To assess the impact of an ACP video decision support tool on patients' knowledge about their EOL care options

- *Hypothesis 2: Patients randomly assigned to the video intervention will report improved knowledge of their EOL care options compared to those randomized to the verbal narrative control*

Aim 3: To assess the impact of an ACP video decision support tool on patients' preferences for EOL care

- *Hypothesis 3: Patients randomly assigned to the ACP video will be more likely to prefer comfort care compared to those randomized to the verbal narrative control arm*
- *Hypothesis 4: Patients randomly assigned to the video intervention will be more likely to forgo cardiopulmonary resuscitation (CPR) and intubation compared to those randomized to the verbal narrative control arm*

Aim 4: To assess the impact of an ACP video decision support tool on patients' documented EOL care preferences

- *Hypothesis 5: Patients randomly assigned to the video intervention will be more likely to have their code status documented in the electronic healthcare record compared to those randomized to the verbal narrative control arm*

BACKGROUND AND SIGNIFICANCE

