Immediately after completing the baseline assessment and randomization, patients assigned to the video intervention arm will view the 3-minute advance care planning video for patients with ESLD on an iPad in the presence of the RA. We will use standardized procedures to minimize the interaction between the RA and patient while the patient is viewing the video. The RA will not be permitted to comment or answer questions while the patient views the video. Patients will be instructed to watch the video once without any interruption and will have no further exposure to the video. If patients have questions about the video or their EOL care options, the RA will instruct them to discuss their questions with their medical team.

The finalized video can be viewed by the IRB at the following link:

<https://vimeo.com/269740750>

Access Code: mghirb

The Control Arm

Immediately after completing the baseline assessment and randomization, patients assigned to the verbal narrative control arm will listen to the same description of the 3 goals of care used in the video arm read out loud by the RA (**Appendix C**). We will use standardized procedures to minimize interaction between the RA and patients during the interview. Specifically, the RA will not be permitted to comment or answer questions while the patients listen to the verbal narrative. Patients will be instructed to ask their physicians any questions they may have about goals of care.

Study Measures

A Randomized Controlled Trial of an Advanced Care Planning Video Decision Support Tool for Patients with End-Stage Liver Disease

Version 9: February 6, 2020

We will administer the following study measures at baseline prior to randomization, and immediately after the video or verbal narrative in the intervention and control group, respectively according to the timeline displayed in **Table 1**:

- *Demographics*: Patients will complete a demographic questionnaire at baseline detailing their age, sex, race/ethnicity, religion, relationship status, educational level, living situation, employment status, and self-reported health status (“Relatively healthy”, “Relatively healthy and terminally ill”, “Seriously ill and not terminally ill”, “Seriously ill and terminally ill”)⁴⁶ (**Appendix D**)
- *EOL Care Preferences*: Patients will report their EOL care preferences as follows: life-prolonging care, limited medical care, comfort care, or unsure. (**Appendix E**)

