- *CPR Preferences*: Patients will report their CPR preferences as follows: “Yes, attempt CPR”, “No, do not attempt CPR”, or “Not sure.” (**Appendix E**)
- *Intubation Preferences*: Patients will report their intubation preferences as follows: “Yes, attempt intubation”, “No, do not attempt intubation”, or “Not sure.” (**Appendix E**)
- *Knowledge Questionnaire*: We will assess patients’ knowledge of goals of care as in previous studies using 5 true/false questions and 1 multiple choice question, each worth 1 point, for a summary score of 0 to 6 (higher score reflects greater knowledge)^{45,47,48} (**Appendix F**)
- *Acceptability of the Video*: For the video intervention arm alone, we will administer 3-items assessing patients’ comfort with watching the video, whether they find the video helpful in their understanding of the EOL care options, and whether they would recommend it to others.⁴⁹ (**Appendix G**)

We will also obtain the following important covariates and outcomes:

- *Disease-related variables*: We will collect variables from the EHR at the time of enrollment, including the etiology of ESLD, presence of clinically-evident decompensating events (ascites, esophageal variceal bleed, hepatic encephalopathy, or multiple), Model of End-Stage Liver Disease Sodium (MELD-Na) score, reason for transplant ineligibility, and clinical comorbidities using the modified Charlson Comorbidity Index.⁵⁰
- *Code Status Documentation in the EMR*: The RA will review the EHR to collect whether clinicians’ documented patients’ code status in the EMR (yes: documented, no: not documented) 3 months after study enrollment.

Table 1: Data Collection Timeline

	Baseline	Post-intervention	3 months post-enrollment
Demographics	X		
Self-Reported Health Status	X		
EOL Care Preferences	X	X	
CPR Preferences	X	X	
Intubation Preferences	X	X	

Knowledge Questionnaire	X	X	
Comfort/Satisfaction with Video (Intervention group only)		X	
Disease-related variables	X		
Code status documentation			X

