We will collect and enter all patient data electronically using Research Electronic Data Capture (REDCap). The REDCap Survey is a tool for building and managing online surveys. Vanderbilt University, in collaboration with a consortium of institutional partners, has developed this software and workflow methodology for electronic collection and management of research and clinical trial data. Our research team has extensive experience using REDCap and will create and design the surveys in a web browser, with institutional information technology support. The REDCap Survey system offers secure, HIPAA compliant, web-based applications that provide an intuitive interface for participants to enter data, with real-time validation rules at the time of entry.

Participants will use tablet computers to complete questionnaires in clinic. If any participants refuse or are unable to complete the questionnaires on the computer, they will be permitted to use hard-copy paper versions. In addition, the patient data collected from the electronic health record will be abstracted throughout the study and directly inputted into REDCap.

Study Outcomes

- **Primary Outcome:** The primary outcome is feasibility. The proposed video intervention will be deemed feasible if at least 60% of eligible patients are enrolled in the study. The 60% feasibility cut-off is commonly used in behavioral intervention studies.⁵¹⁻⁵³
- **Secondary Outcomes:** The secondary outcomes will include patients' comfort/satisfaction with the video, patients' stated post-intervention EOL care preferences categorized as four options: Life-prolonging care, limited medical care, comfort care, or unsure; individual preferences for CPR and intubation before and after intervention in the verbal narrative and video groups; and change in knowledge scores after receiving the verbal narrative or video

Sample Size Calculation

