We will randomize up to 70 patients with ESLD for this project. The primary endpoint of the study is feasibility. We chose the sample size of 70 patients based on the feasibility of completing the project during the proposed timeframe and the ability to assess the preliminary efficacy of the intervention. Consistent with the behavioral intervention literature, at least 20 patients are needed in each group in a pilot study to estimate a parameter.^{54,55} Therefore, the proposed sample size will provide us with preliminary data that can be utilized to determine the effect size and adequately power future randomized trials. This is a commonly utilized study design for pilot testing of behavioral interventions and is consistent with the National Institute of Health Stage Model for Intervention Development. While the feasibility of the intervention can be assessed using a single-arm design, preliminary efficacy is better assessed utilizing a control group as we are proposing in this trial.

A Randomized Controlled Trial of an Advanced Care Planning Video Decision Support Tool for Patients with End-Stage Liver Disease

Analysis Plan

We will report baseline demographic and clinical characteristics of all study participants using means and proportions to describe continuous and categorical variables, respectively. Because this is a pilot study, we will use conservative ($\alpha = 0.05$) and liberal ($\alpha = 0.20$) critical values to assess statistical significance between the two arms in this pilot study.

Aim 1: The primary endpoint of the proposed study is feasibility. The proposed video intervention will be deemed feasible if at least 60% (95% CI +/- 13.6%) of eligible patients are enrolled in the study and complete at least 60% of the intervention sessions. The proposed video intervention will be deemed acceptable if at least 75% of patients randomized to the intervention arm report satisfaction and comfort with the video.

Aim 2: Changes in knowledge scores from before and after the intervention will be compared between the two groups using two-sample t-tests.

Aim 3: Post-intervention EOL care preferences (life-prolonging care, limited medical care, and comfort care), CPR preferences, and intubation preferences will be compared between the two groups using Fisher's exact tests. The change in CPR and intubation preferences before and after the intervention within each group will be compared using McNemar tests.

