APPENDIX E: End of Life Care, Cardiopulmonary Resuscitation, and Intubation Preferences

1. Imagine that your liver disease became very advanced and that you became very ill and in need of medical treatment, which general approach would you want provided?
 Life-prolonging care
 Limited medical care
 Comfort care
 Unsure
2. If your liver disease were very advanced and you were to get so sick that your heart stopped beating, would you want doctors to do chest compressions and CPR to try to make your heart start again?
 Yes, attempt CPR
 No, do not attempt CPR
 Not sure
3. If your liver disease were very advanced and you were to get so sick that you could not breathe on your own, would you want doctors to place you on a breathing machine to help you breathe?
 Yes, attempt intubation
 No, do not attempt intubation
 Not sure

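### The Aim 3 analysis does not fix the contrasts in Hypotheses 3 and 4, lists three end-of-life categories where the outcome has four, and gives McNemar no two-level rule

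*Combined protocol and SAP*

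**What the plan says.** Specific Aims states two directional hypotheses about preferences. In Hypothesis 3, patients shown the video "will be more likely to prefer comfort care compared to those randomized to the verbal narrative control arm". Hypothesis 4 reads "Patients randomly assigned to the video intervention will be more likely to forgo cardiopulmonary resuscitation (CPR) and intubation" than control patients. Each points to one answer on its scale.

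Study Measures sets the scales: "Patients will report their EOL care preferences as follows: life-prolonging care, limited medical care, comfort care, or unsure". CPR and intubation answers have three levels: yes, no, not sure. Appendix E uses the same options, with "No, do not attempt CPR" as the declining answer for CPR. Under Study Outcomes, the secondary outcome is patients' "stated post-intervention EOL care preferences categorized as four options: Life-prolonging care, limited medical care, comfort care, or unsure".

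The Analysis Plan for Aim 3 says "Post-intervention EOL care preferences (life-prolonging care, limited medical care, and comfort care), CPR preferences, and intubation preferences will be compared between the two groups"; the method it names is Fisher's exact test. For change within an arm it adds: "The change in CPR and intubation preferences before and after the intervention within each group will be compared using McNemar tests". Comparisons between arms are judged at alpha 0.05 and at 0.20. The plan does not say which level is contrasted with which, or what happens to the unsure and not sure answers.

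**The concern.** There are three gaps.

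- **Contrast.** A Fisher test across all categories is valid, but its null is that the whole distribution is the same in both arms. It can reject because patients moved between life-prolonging and limited care, or between yes and not sure, with no difference in the answer that the hypothesis names.
- **Categories.** The Analysis Plan's list of three conflicts with the four-option outcome. If the list is followed literally, unsure patients drop out because of an answer given after randomization, which the video may itself affect.
- **McNemar.** The test needs paired two-level data. With three levels it cannot be run until someone decides where not sure belongs.

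Each choice could be made after the results are seen. The Sample Size section says the trial will supply preliminary efficacy data to determine the effect size for later trials. For a preference outcome, that requires a defined proportion and its difference between arms, which a multi-category p-value does not give.

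**Working it through.** The documents give no assumed rate, power or effect size for Aim 3, so there is no figure to reproduce. The first step is to compare the texts.

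| Item | Hypotheses, Measures, Outcomes, Appendix E | Analysis Plan, Aim 3 |
|---|---|---|
| End-of-life preference | four options, including unsure | three listed, unsure absent |
| Hypothesis 3 | more comfort care | Fisher test on preferences, no target level |
| Hypothesis 4 | more patients declining CPR and intubation | Fisher test on preferences, no target level |
| CPR and intubation answers | three levels | McNemar, no rule for two levels |

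The second step is to ask whether the gaps can change a result. Up to 70 patients at 1:1 gives 35 per arm. **All counts and rates below are assumptions.** Tests are two-sided and exact unless stated.

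**End-of-life example** (life-prolonging / limited / comfort / unsure): control 14/7/7/7, video 13/7/14/1.
- Three categories, unsure dropped (28 v 34 patients): p = 0.459.
- Four categories: p = 0.082.
- Comfort care v all others, 7/35 v 14/35: p = 0.117. The risk difference is 0.40 - 0.20 = 0.20 (Newcombe 95% CI -0.015 to 0.392).

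At the plan's 0.20 threshold, the last two are significant and the first is not.

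**Rejection rates** from 4,000 simulated trials per scenario, shown as three-category / four-category / comfort v rest:

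| Control v video | alpha 0.05 | alpha 0.20 |
|---|---|---|
| Comfort equal, 20 points from life-prolonging to limited: .45/.20/.25/.10 v .25/.40/.25/.10 | 0.44 / 0.39 / 0.02 | 0.71 / 0.67 / 0.13 |
| Comfort equal, 40 points: .55/.10/.25/.10 v .15/.50/.25/.10 | 0.99 / 0.98 / 0.03 | 1.00 / 1.00 / 0.12 |
| Scenario 1, comfort rises: .40/.25/.20/.15 v .25/.20/.50/.05 | 0.57 / 0.66 / 0.69 | 0.81 / 0.87 / 0.88 |
| Scenario 2, unsure falls a lot: .35/.20/.20/.25 v .30/.20/.45/.05 | 0.28 / 0.69 / 0.53 | 0.56 / 0.89 / 0.78 |

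In the first two rows Hypothesis 3 is false, yet the multi-category tests reject often. In scenario 2, dropping unsure cuts power from 0.69 to 0.28.

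**CPR example** (yes / no / not sure): control 20/12/3, video 11/12/12. The three-level Fisher test gives p = 0.018. The no answer is 12/35 in each arm, so no v other gives p = 1.0.

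**McNemar example**, one arm: 8 patients move from not sure to no, 3 from yes to no, 2 from no to yes, and the rest do not change. The exact p-value is 2 × P(X ≤ min(b, c)) with X ~ Binomial(b + c, ½), capped at 1.
- No v other: 8 + 3 = 11 against 2. p = 2 × (1 + 13 + 78)/2¹³ = 184/8192 = 0.022.
- Yes v other: 3 against 2, p = 1.0.
- Not sure dropped: 3 against 2, p = 1.0.
- Bowker's test on the 3×3 table: (3 - 2)²/5 + (8 - 0)²/8 + 0 = 8.2 on 3 df, asymptotic p = 0.042.

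**The case against.** The hypotheses already fix the target answer and its direction, so an analyst is not free to choose any contrast. That is right, and the between-arm test is underspecified rather than invalid. But the hypotheses do not say whether the table is 2×2 or larger, or where unsure goes.

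The three-category list may be shorthand for the three-part goals-of-care framework, since nothing states that unsure is excluded. That is possible, so this is a conflict of wording, not a planned exclusion. The two passages still have to agree.

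In the end-of-life example, the four-category test and the comfort-care contrast give the same decision at both thresholds. True: that example bears on the category conflict. The case for a named contrast rests on the scenarios with comfort care held equal, which no documented rate supports, and the 40-point shift is extreme. When comfort care does rise (scenario 1), the two tests have similar power (0.66 and 0.69).

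McNemar is a within-arm test and decides neither hypothesis. That limits the consequence, but the test still cannot be run as written.

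The effect size for later trials could come from the knowledge score instead. The plan does not say which outcome will supply it, so the preference outcomes are one candidate.

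**Conclusion.** All three parts hold. The category conflict and the McNemar gap are errors in the text as written. The missing contrasts are an underspecification that is cheap to close. The size depends on assumed rates at 35 per arm. With comfort care equal and a 20-point move between the other two care options, a multi-category test rejects in 39% to 44% of trials at alpha 0.05, while the contrast in Hypothesis 3 rejects in about 2%. In the McNemar example, the coding alone moves p from 0.022 to 1.0. That the choices are open follows from the text and does not depend on these rates. The primary feasibility conclusion and the sample size do not change. This should be corrected, but it does not threaten the trial.

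**What to change.** In the Analysis Plan for Aim 3:

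1. List all four end-of-life options, in agreement with Study Outcomes.
2. For Hypothesis 3, prespecify Fisher's exact test of comfort care v all other answers, with unsure counted as not comfort care, in all randomized patients. Report the risk difference with its 95% CI.
3. For Hypothesis 4, do the same for the do-not-attempt answer v all other answers, separately for CPR and for intubation. Study Outcomes already speaks of individual preferences for each.
4. State how a missing post-intervention answer is handled, because the Appendix A script lets patients skip questions or stop.
5. Report the full four-level and three-level distributions by arm. The four-category test can be kept as supportive.
6. Run the within-arm McNemar on no v not no, as description. Bowker's test on the 3×3 table is an alternative; choose one in advance.

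Baseline adjustment is at most an optional sensitivity analysis.

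The cost is a few sentences, since Table 1 already schedules collection of these answers. The two-level contrast shows less of the movement among other answers, and it can lose power when unsure changes a lot: 53% against 69% for the four-category test at alpha 0.05 in scenario 2.

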Our proposed project is a single-center randomized controlled trial to assess the feasibility, acceptability and preliminary efficacy of an ACP video decision support tool versus a verbal narrative alone on EOL care preferences in transplant ineligible patients with ESLD in the outpatient setting. We will recruit up to 70 consecutive patients with ESLD who receive ambulatory care at the MGH Liver Center for this study. Patients will be randomized in a 1:1 fashion (**Figure 1**). To ensure that patients in this sample received longitudinal care (ruling out

A Randomized Controlled Trial of an Advanced Care Planning Video Decision Support Tool for Patients with End-Stage Liver Disease

Version 9: February 6, 2020

those being seen for second-opinion consultation), we will only include those patients who have had two or more visits to the MGH Liver Center.

Eligibility Criteria

Our proposed project is a single-center randomized controlled trial to assess the feasibility, acceptability and preliminary efficacy of an ACP video decision support tool versus a verbal narrative alone on EOL care preferences in transplant ineligible patients with ESLD. We will recruit up to 70 consecutive adult patients with ESLD who receive care at MGH for this study. Patients will be randomized in a 1:1 fashion (see **Schema for further details**).

Eligibility Criteria

All patients with ESLD who are \geq 18 years of age seen at the Massachusetts General Hospital will be screened for study participation. Our study population is defined as patients with cirrhosis complicated by at least one of the following clinically-evident decompensating events: 1) ascites; 2) hepatic encephalopathy; or 3) history of gastroesophageal variceal hemorrhage - which portends a poor prognosis.⁴⁰ Only patients who are deemed ineligible for liver transplantation by either their primary hepatologist or the inpatient hepatology consult service attending will be eligible for this study as this is a patient population for whom the diagnosis of ESLD is a terminal one.

Patients Inclusion Criteria:

[figure not shown]
1. \geq 18 years of age with an established diagnosis of ESLD
2. Patient must have either 1) primary hepatologist at the MGH Liver Center or an MGH-affiliated primary care physician, or 2) a previous inpatient admission at MGH
3. Deemed ineligible for liver transplantation as determined by the primary hepatologist or the inpatient hepatology consult service attending

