introduces a framework for choices of medical care at the EOL including: 1) life-prolonging care; 2) limited medical care; and 3) comfort care. The visual images illustrating life-prolonging care include interventions that are available in a modern-day hospital such as CPR, mechanical ventilation, and treatment in the ICU. Scenes include an ICU with a ventilated patient being tended to by respiratory therapists, a simulated code conducted with clinicians illustrating chest compressions, CPR and intubation, and the administration of medications through a central venous catheter. For the second option, limited medical care, the narrator explains the goal of care is to pursue treatment for medical conditions, but avoid intensive medical interventions at the EOL. This type of care would include hospital care, intravenous medications, and antibiotics, but not CPR or ICU care. Visual images include a patient getting medicine via a peripheral venous catheter, scenes from a typical medical ward, and a patient wearing a nasal cannula to receive oxygen and breathing treatments. For the third option, comfort care, the narrator describes the goal of care as relieving symptoms and utilizing medical care that would only be used to provide comfort. Visual images include a patient on hospice care at home receiving pain medications, a patient with a respiratory face mask receiving oxygen at home, and an attendant assisting a patient with self-care. All three sequences of video images accompanying the narration attempt to help the viewer imagine the experience and likely outcomes of receiving these medical interventions at the EOL. The video was filmed and edited by the research team without the use of prompts or stage directions to convey a candid realism in the style known as *cinema vérité*. All patients included in the video (or their proxies) gave consent to be filmed.

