APPENDIX C: Verbal Narrative Transcript

I'd like to talk about choices for medical care when patients are very sick and in the hospital. I will explain 3 basic types of medical care. This is a way for you to start thinking now about the type of care you would want should you get very sick or not able to speak up for yourself. The reason that this is important is that people have very different ideas about what they want.

There are three basic types of medical care for people who are very sick. These are life prolonging care, limited medical care, and comfort care. Here is more to know:

Life prolonging care.

The first option is life prolonging care.

The goal of this type of care is to "prolong life," meaning that doctors will do everything they can to keep you alive. This can include trying cardiopulmonary resuscitation (or CPR) to restart your heart after it stopped beating. To do this, the doctor presses hard on your chest and uses a device to give your heart an electric shock.

If you want the doctor to try CPR, you must also agree to be on a ventilator (or breathing machine) if needed. When getting a ventilator, the doctor puts a tube down your throat. One end of the tube goes into your lungs and the other connects to a machine that pushes air into them. You cannot eat or talk while on a ventilator. You likely will also need such strong medicines that you must stay in the hospital's Intensive Care Unit (or ICU).

With life prolonging care, you agree to CPR and a ventilator in hopes for a longer life. But for most patients with advanced liver disease, CPR does not work. CPR also will not cure your liver disease or get you back to the level of health you had before your heart stopped.

Limited medical care.

The second option is limited medical care.

This is when people agree to just certain kinds of medical care. For instance, with limited medical care you might get medicine for treatable problems like fluid in the abdomen or infections around the stomach area. You might be admitted into the hospital and get fluids or medications through an IV tube that goes into your vein. But with limited medical care, you do not want doctors to try CPR or put you on a breathing machine--even if that means that without those treatments, you might die.

Comfort care.

The third option is comfort care.

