The goal of this type of care is to increase comfort and reduce symptoms, but not to prolong life. People who choose this type of care might be at home, or in a hospice or nursing home. With comfort care the healthcare team can treat symptoms like breathing problems, nausea, and pain. But comfort care does not include CPR and breathing machines. It also does not include going to the hospital, unless the doctor thinks you will be more comfortable there. The goal of this type of care is to increase comfort and relieve pain.

I hope this helped you learn more about choices of medical care when people are very sick. Think about what matters to you. Discuss this with your family. Make sure to also talk with your doctor who may suggest a certain type of medical care for you. Once you decide what you want, tell your doctor and family. It is okay to later change your mind so long as you discuss that with your doctor and family. They can help protect your rights and wishes about medical care.

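### Aim 3's overall Fisher test on end-of-life care preference does not answer directional Hypothesis 3 and gives no effect size; a comfort-care difference with confidence interval should be pre-specified beside it

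*Combined protocol and SAP*

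**What the plan says.** Hypothesis 3 (Specific Aims) is directional and concerns one option: "Patients randomly assigned to the ACP video will be more likely to prefer comfort care compared to those randomized to the verbal narrative control arm".

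The Analysis Plan, Aim 3, gives the only between-arm analysis of the item, by Fisher's exact test: "Post-intervention EOL care preferences (life-prolonging care, limited medical care, and comfort care), CPR preferences, and intubation preferences will be compared between the two groups using" that test. It names no ordered test, no contrast of comfort care against the rest, and no effect estimate.

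The materials shown to patients describe three options of falling intensity, although the documents never call them an ordinal scale:
- life-prolonging care, "meaning that doctors will do everything they can to keep you alive" (Appendix C);
- limited care: "This type of care would include hospital care, intravenous medications, and antibiotics, but not CPR or ICU care" (The Intervention Arm);
- comfort care: "But comfort care does not include CPR and breathing machines. It also does not include going to the hospital, unless the doctor thinks you will" (Appendix C; the sentence ends with an exception for the patient's comfort).

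Study Outcomes and Appendix E add a fourth answer, 'unsure', which the Aim 3 list leaves out.

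On size and level: "We will randomize up to 70 patients with ESLD for this project"; "Patients will be randomized in a 1:1 fashion"; and "we will use conservative ($\alpha = 0.05$) and liberal ($\alpha = 0.20$) critical values to assess statistical significance between the two arms". The Sample Size Calculation gives no power figure. It says the data should serve to determine an effect size and to power later trials.

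**The concern.** With three columns, Fisher's test asks whether the two arms differ in any way. Relabelling or reordering the options leaves the p-value unchanged, so the test cannot tell movement into comfort care from movement between the other two options. Hypothesis 3 is about the first of these only.

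Two things are at stake. A significant Aim 3 result could be reported as support for Hypothesis 3 when it is not. And the pilot would end with a p-value for this item where its own sample-size rationale asks for an effect size.

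**Working it through.** **Inputs.** From the documents: at most 70 patients, 1:1, hence 35 per arm; alpha 0.05 and 0.20; three options as listed in Aim 3. Assumed, because the documents are silent: two-sided tests and all category proportions. The plan states no power or effect size for this item, so there is no figure to reproduce.

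**Formulas.** Let a_j be the control-arm count and c_j the total count in option j. Given the margins, P(table) = ∏ C(c_j, a_j) / C(70, 35).
- Fisher 2x3: p is the sum of P over tables no more probable than the observed one. The product does not depend on the order of the columns, so neither does p.
- Exact Wilcoxon: midrank r_j = (sum of c_k for k < j) + (c_j + 1)/2 and W = Σ a_j r_j. Then p is the sum of P over tables with |W − 35×71/2| at least as large as observed.
- Power is the sum of the two arms' multinomial probabilities over all tables that reject. Very improbable tables were dropped; those kept carry more than 99.99% of the probability.

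**Results**, rejection % at alpha 0.05, 35 per arm, life-prolonging/limited/comfort. The last column is a 2x2 Fisher test of comfort care against the rest.

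| Pattern | Control vs video | Fisher 2x3 | Exact Wilcoxon | Comfort vs rest |
|---|---|---|---|---|
| No effect | 40/30/30 in both | 4.7 | 4.5 | 2.8 |
| Comfort unchanged | 40/30/30 vs 20/50/30 | 41.7 | 18.8 | 2.8 |
| | 50/30/20 vs 30/50/20 | 36.2 | 23.5 | 2.5 |
| | 50/30/20 vs 25/55/20 | 54.4 | 34.5 | 2.5 |
| Limited to comfort only | 40/30/30 vs 40/10/50 | 52.7 | 15.5 | 31.2 |
| Graded | 40/30/30 vs 25/30/45 | 24.2 | 30.4 | 18.7 |
| | 40/30/30 vs 20/30/50 | 41.7 | 50.3 | 31.2 |
| | 50/30/20 vs 25/35/40 | 53.4 | 62.9 | 35.7 |
| Comfort drawn proportionally | 40/30/30 vs 28.6/21.4/50 | 30.5 | 32.7 | 31.2 |
| | 50/30/20 vs 35/21/44 | 46.9 | 44.4 | 49.4 |
| | 30/50/20 vs 22.5/37.5/40 | 34.6 | 33.4 | 35.7 |
| | 20/50/30 vs 14.3/35.7/50 | 30.5 | 33.5 | 31.2 |

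Separate simulation of the first and third comfort-unchanged rows gave 43% and 53% for Fisher, which agrees within simulation error.

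**Reading the table.**
1. The rows 40/30/30 vs 20/50/30 and 40/30/30 vs 20/30/50 have the same Fisher power, 41.7%. In one, comfort care does not move; in the other it rises by 20 points. Fisher cannot separate them.
2. With comfort care unchanged, Fisher rejects 36% to 54% of the time at alpha 0.05, and 63% to 79% at alpha 0.20. These are correct rejections of equal distributions, but they do not support Hypothesis 3.
3. Wilcoxon minus Fisher: graded rows, +6.2, +8.6 and +9.5 points; proportional rows, between −2.5 and +3.0; adjacent-option rows, 36.2 − 23.5 = 12.7 lost at the least and 52.7 − 15.5 = 37.2 at the most.
4. Under a proportional-odds shift from 40/30/30, Fisher vs exact Wilcoxon is 25.8% vs 32.4% (odds ratio 2), 56.7% vs 66.7% (3) and 77.1% vs 85.0% (4). Over six assumed control distributions the gain is only 2 to 3 points at an odds ratio of 1.5.

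**One table as illustration.** Control 10/15/10 vs video 15/5/15 gives Fisher p = 0.035 and Wilcoxon p = 1.0. Fisher is significant although life-prolonging and comfort care each gained five patients.

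**Precision of the proposed estimate.** For 30% vs 50% comfort care, the approximate 95% half-width is 1.96 × √(0.30×0.70/35 + 0.50×0.50/35) = 0.225, or 22.5 points.

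**The case against.** Much of the other side stands. Fisher's test holds its level (4.7% in the null case). The item is one of several secondary outcomes in a pilot whose primary outcome is feasibility, the sample size was not set by power, and three percentages per arm would show direction to the eye. An overall test is a reasonable hedge when the pattern of response is unknown.

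A reader might infer that, because the options fall in intensity, Fisher's test should be replaced by an ordered test and that the plan forfeits 5 to 10 points of power. The documents do not support that. They give no proportions and do not say that the shift will be graded, and the gain vanishes or reverses under other plausible patterns. A rank test also does not match Hypothesis 3: it rejects 34.5% of the time for 50/30/20 vs 25/55/20, where comfort care is the same in both arms. Nor do the documents give 'unsure' a rank; placing it with life-prolonging care would count a move from uncertain to limited care as benefit.

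The objection does not remove two facts: the planned test does not address the stated hypothesis, and no effect estimate is specified for an item meant to inform later trials.

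**Conclusion.** The point holds as one of fit and reporting, not of validity. A significant Fisher result for this item would not by itself support Hypothesis 3: with comfort care unchanged it rejects about 42% and 54% of the time in the two main scenarios. The plan also specifies no effect size where its own rationale wants one. The figures rest on assumed proportions, 35 per arm, two-sided tests and the three options named in Aim 3; the mismatch between test and hypothesis does not depend on them. The order of the options justifies a supplementary analysis, not a replacement test. The change is worth making but moderate in weight, since the outcome is secondary.

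**What to change.** In the Analysis Plan, Aim 3, before preferences are compared by arm:
- Keep Fisher's exact test as the overall comparison of the care-preference item, and state which answers enter the table.
- Name as the analysis that answers Hypothesis 3 the percentage choosing comfort care in each arm, among all randomised patients with a post-intervention answer and with 'unsure' counted as not comfort care. Report the difference and its confidence interval, with the interval method and level stated.
- Add a supplementary ordinal analysis on the three ordered options: exact Wilcoxon test and a common odds ratio with confidence interval. Include sensitivity analyses that place 'unsure' with life-prolonging care and in the middle.
- State that a significant overall Fisher result is not, by itself, evidence for Hypothesis 3.

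Cost: a few sentences, standard software, no new data or patients, and one more secondary comparison. The comfort-versus-rest contrast has less power than the 2x3 Fisher test for many graded shifts (for example 31.2% vs 41.7% for 40/30/30 vs 20/30/50), and its interval will be wide at this size. The proportional-odds assumption can barely be checked with 35 per arm, which is a further reason to keep that model supplementary.
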